Statistical Analysis Plan

Title of Study: Management of Persistent Epistaxis Using Floseal

Hemostatic Matrix

Protocol ID: 6601059

Date of Document: August 22, 2015

Date Modified: October 12, 2018

Sample Size:

An *a priori* sample size was calculated using a non-inferiority limit (d) set at 25%, significance level (α) of 5% and power of 80%. We assumed that success in each group will be approximately 93% based on the literature examining anterior nasal packing in ideal conditions and considering our selection criteria in the Floseal® (Baxter, USA) population. Attrition will be assumed to be 0% due to the short duration of treatment. This should yield 26 participants with 13 patients in each study arm.

Statistical Analysis of Clinical End-points:

This is a non-inferiority trial. A non-inferiority design was chosen due to the anticipated improvement in patient comfort and potential decreased cost thus making the experimental arm a preferred option if non-inferiority can be demonstrated in terms of hemostasis. Further, based on existing literature we do not anticipate a significant difference in terms of efficacy between these two groups. All dichotomous categorical variables will be analyzed by means of the Fisher's exact test. Mean age, CCI and VAS pain scores will be compared using the non- parametric Mann-Whitney U Test.

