Management of Persistent Epistaxis Using Floseal Hemostatic Matrix

PROTOCOL IDENTIFYING NUMBER 001

PROTOCOL VERSION DATE June 8, 2015

GENERAL INFORMATION

Name and title of the investigators and sub-investigators responsible for the trial with address and phone numbers

[name] [name]

[name] [contact]

[name]

[name] [contact]

[name] BSc.

[name] [contact] [contact]

| Title | Management of Persistent Epistaxis using Floseal Hemostatic Matrix |
|--|---|
| Short Title | Floseal Epistaxis Study |
| Protocol Number | 001 |
| Phase | Phase 4 Clinical Trial |
| Methodology | Randomized open-label Trial |
| Study Duration | 1 Year |
| Study Center(s) | Single-Center, University of Alberta |
| Objectives | We wish to observe the effectiveness of Floseal Hemostatic Matrix in aborting persistent epistaxis with the end of bleeding being our primary outcome. We also wish to include measures of patient comfort and cost analysis of epistaxis treatment. |
| Number of Subjects | 60 |
| Diagnosis and Main Inclusion Criteria | Adult patients presenting for Otolaryngology Head and Neck Surgery consult in the Emergency Department with persistent epistaxis. |
| Study Product, Dose, | Floseal Hemostatic Matrix, 5mL |
| Duration of administration | 30 Minutes |
| Reference therapy | Standard nasal packing using gauze by a trained Otolaryngology resident |
| Statistical Methodology | This study is powered based on a non-inferiority analysis to compare the efficacy of Floseal at achieving hemostasis. We will perform standard chi-square statistical analysis to determine the significance of these outcomes. |

Study Summary

Table of Contents

| 1 | | BACKGROUND | .1 |
|----|-----|---|---------------------|
| | 1.1 | INVESTIGATIONAL AGENT | .1 |
| | 1.2 | PRECLINICAL DATA | .1 |
| | 1.3 | Risk/Benefits | .1 |
| | 1.4 | DOSE RATIONALE | .1 |
| | 1.5 | TRIAL CONDUCT | .1 |
| | 1.0 | POPULATION. | .2 |
| | 1./ | LII EKA I UKE | .2 |
| 2 | | TRIAL OBJECTIVES | .2 |
| 3 | | TRIAL DESIGN | .2 |
| | 3.1 | PRIMARY STUDY ENDPOINTS/SECONDARY ENDPOINTS | .2 |
| | 3.2 | Study Design/Type | .2 |
| | 3.3 | RANDOMIZATION | .3 |
| | 3.4 | TRIAL TREATMENT | .3 |
| | 3.5 | DURATION | .3 |
| | 3.6 | DISCONTINUATION | .4 |
| | 3.7 | DATA IDENTIFICATION | .4 |

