1.5 Trial Conduct

This study will be conducted in compliance with the protocol approved by the University of Alberta Health Research Ethics Board (HREB), and according to Good Clinical Practice standards. No deviation from the protocol will be implemented without the prior review and approval of the HREB except where it may be necessary to eliminate an

immediate hazard to a research subject. In such case, the deviation will be reported to the HREB as soon as possible.

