7.3 Significance

This is a non-inferiority trial with a power of 0.8, a non-inferiority limit of 5% and a significance level of P < 0.05.

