7.5 Deviation Reporting

In the case that any changes to the statistical analysis of this trial may arise they will be fully disclosed. Any deviation from the original statistical plan will be amended and justified in the protocol and in the final report.

8 Direct Access to Source Data/Documentation

Throughout the study if direct access data is required for audit or other trial-related monitoring, it can be obtained by written request to [name]. This includes access by any regulatory agency such as the University of Alberta HREB.

9 Quality Control and Quality Assurance

Data from the direct care team will be obtained in paper form and be scanned or otherwise transferred to electronic data kept on the research computer. Interim analysis will be done by the research team to ensure that data collection is continuing as per the protocol. The study coordinator ([name]) will review that data obtained following each patient enrolled in the study and ensure that it is being recorded in compliance with this protocol and good clinical practice requirements.

10 Ethical Considerations

This study will be conducted according to Canadian and international standards of Good Clinical Practice for all studies. Applicable government regulations and University of Alberta research policies and procedures will also be followed.

This protocol and any amendments will be submitted to the University of Alberta HREB for formal approval to conduct the study. The decision of the HREB concerning the conduct of the study will be made in writing to the investigator.

All subjects for this study will be provided a consent form describing this study and providing sufficient information for subjects to make an informed decision about their participation in this study. This consent form will be submitted with the protocol for review and approval by the HREB. The formal consent of a subject, using the HREB-approved consent form, will be obtained before that subject is submitted to any study procedure. This consent form must be signed by the subject or legally acceptable surrogate, and the investigator-designated research professional obtaining the consent.

11 Data Handling and Record Keeping

For confidentiality purposes all data for this study will be coded and de-identified and kept on an encrypted secured database in the personal office of [name].

12 Supplements

Comfort Questionnaire

Patient Name: _____ Researcher Filling out this form: _____

In Person

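### The protocol sets the non-inferiority limit at 5% and the SAP at 25%; the SAP calls its calculation a priori but neither dates nor justifies the 25%, and the choice changes the verdict

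*SAP*

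**What the plan says.** **Protocol.** The version date is given as "PROTOCOL VERSION DATE June 8, 2015". Section 7.3 reads: "This is a non-inferiority trial with a power of 0.8, a non-inferiority limit of 5% and a significance level of P < 0.05". Section 7.2 plans 60 patients, 30 per arm. Section 7.5 sets the rule for changes: "Any deviation from the original statistical plan will be amended and justified in the protocol and in the final report". Section 1.5 adds: "No deviation from the protocol will be implemented without the prior review and approval of the HREB", with an exception for immediate hazards.

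**SAP.** The header gives a document date of August 22, 2015 and then "Date Modified: October 12, 2018". The Sample Size paragraph reads: "An *a priori* sample size was calculated using a non-inferiority limit (d) set at 25" per cent, with "significance level (α) of 5% and power of 80" per cent. It assumes 93% success in each arm and no attrition, and arrives at 26 patients, 13 per arm.

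The SAP explains why a non-inferiority design was chosen and where the 93% comes from. It gives no reason for 25%, does not mention the protocol's 5% or its 60 patients, and does not say what was changed in 2018.

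**The concern.** A non-inferiority limit protects the conclusion only if it was fixed before anyone could see which limit the data would meet. Here the limit differs fivefold between the two governing documents, and the wider one is in a file last modified more than three years after the protocol date, in a trial planned to last one year.

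The trial is open-label (section 3.3), the research team reviews data after each enrolled patient (section 5.2), and section 9 mentions interim analysis by the same team. Nothing describes a separation between people who know outcomes and people who edit the SAP. If the 25% entered in 2018, it could have been set with outcomes known. If it entered in August 2015, about 11 weeks after the protocol, it may be a genuine prior choice whose documentation is incomplete. The supplied texts do not tell these cases apart.

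At stake is the primary conclusion: the same data can be called non-inferior under the SAP and not under the protocol.

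**Working it through.** **Inputs.** Success 93% in both arms, limit 25%, alpha 5%, power 80%, attrition 0%, 13 per arm (SAP, Sample Size). Limit 5%, power 0.8, 30 per arm (protocol 7.2 and 7.3). Neither document states whether alpha is one-sided or names a confidence interval method, so I show two methods.

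**1. Reproduce the SAP's figure.** n per arm = 2p(1-p)(z₁₋α + z₀.₈)² / d², unpooled variance, true difference zero.
- One-sided 5%: 2 × 0.93 × 0.07 × (1.645 + 0.842)² / 0.25² = 12.88, so 13 per arm and 26 in total. This matches exactly.
- One-sided 2.5%: 16.35, so 17 per arm. This does not match.

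So 25% is a working input, not a typing slip, and the SAP's alpha is one-sided 5%, which corresponds to a 90% two-sided interval.

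**2. The same formula at the protocol's 5%.** At 93% success, d = 0.05 gives 322 per arm (one-sided 5%) or 409 (one-sided 2.5%). The protocol gives no success rate; 30 per arm would be enough only if success were about 99.4% (one-sided 5%) or 99.5% (one-sided 2.5%) in both arms. By normal approximation at one-sided 5%, power against the 5% limit is 12.6% with 13 per arm and 18.8% with 30 per arm. Against 25%, 13 per arm has 80.3%.

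**3. How often the limit decides the verdict.** Enumerate every pair of success counts at 13 v 13, weight by binomial probabilities with p = 0.93 in both arms, and check whether the lower limit of the 90% interval for Floseal minus packing clears each limit.

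| 90% interval | Clears -25 points | Clears -5 points | Verdict depends on the limit |
|---|---|---|---|
| Newcombe | 66.2% | 9.3% | 66.2 - 9.3 = 56.9% |
| Wald | 81.0% | 39.3% | 81.0 - 39.3 = 41.7% |

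The Wald figure at -5 is inflated because that interval has zero width at 13/13 v 13/13, a result with probability 15.2%. With 95% Newcombe intervals the two pass rates are 48.7% and 2.3%.

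**4. Particular results (90% Newcombe lower limit).**
- 13/13 v 13/13: -17.2 points. Passes at 25%, fails at 5%.
- 12/13 v 12/13: -21.4 points. Passes at 25%, fails at 5%.
- 12/13 Floseal v 13/13 packing: -28.2 points. Fails at both.
- For comparison, 30/30 v 30/30: -8.3 points. Fails at 5% even at the protocol's size.

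**5. What a pass at 25% means.** The edge of the limit is 93 - 25 = 68% success on Floseal, that is, 32% needing additional measures against 7%. The same enumeration at true rates 0.68 v 0.93 gives a pass in 6.0% of trials (Newcombe) or 7.6% (Wald), close to the nominal 5%.

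**The case against.** Several stronger readings are tempting, and the documents do not support them.

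- *That the limit was widened after the results were seen.* The SAP carries an August 2015 date, and 25% may have stood in it from then, in which case the a priori label would be true whatever the state of the protocol. No enrolment, completion or analysis date is given, and the section 5.2 review is described as a check on conduct and recording, not as a comparison of arms.
- *That no justification or amendment exists.* The only protocol supplied is dated June 2015, before the SAP, and could not contain a later amendment. The final report, the other place that section 7.5 names, is not supplied. Only absence from these documents can be stated.
- *That 25% would let a true 32% v 7% difference in failures be called non-inferior.* That difference would pass only about 6% to 8% of the time. Under Newcombe no result with fewer successes on Floseal than on packing passes at all.
- *That the limit alone settles the answer.* Even with equal true success, about 34% of trials fail at 25% under Newcombe (19% under Wald). The data still matter.
- *That 5% is the ethics-approved standard to return to.* No approval record for this version is supplied, and 5% was never workable with 60 patients at 93% success.

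The magnitude also depends on the interval, and neither Newcombe nor Wald is in the plan, which names only Fisher's exact test. All of this stands. It leaves untouched the conflict between the two limits, the missing date, the missing rationale, and the finding that the limit changes the verdict in a large share of trials under either interval.

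**Conclusion.** The concern holds as a contradiction in the decision threshold, with an undated and unexplained value in the later document. A choice made after outcomes were known is possible and cannot be excluded, but it is not shown.

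If true success is 93% in both arms and 13 patients per arm are analysed, the verdict turns on which limit applies in about 57% of trials (Newcombe) or 42% (Wald), using 90% intervals to match the one-sided 5% that reproduces the SAP's sample size. Because this governs the primary conclusion, it should be settled before any claim of non-inferiority is made.

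The 5% limit is not a realistic criterion at this size: the formula asks for about 322 per arm, and even 13/13 v 13/13 misses it under Newcombe. Failing 5% would therefore be inconclusive and would not show that Floseal is inferior.

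**What to change.** 1. Reconcile the protocol and SAP on one limit and the sample size that goes with it, stating that alpha is one-sided 5% if that is what was meant.
2. In the SAP, state the date on which 25% was adopted, how many patients had known outcomes on that date, and what the October 2018 modification changed. Give the rationale for 25% in a protocol amendment and in the final report, as section 7.5 requires; if an amendment already exists, cite it.
3. If 25% was not fixed before the first outcome, delete the a priori label and call the 25-point result post hoc.
4. In every case, report the lower confidence limit for the difference in hemostasis, by a named interval method, against both 5% and 25%.
5. Word a pass at 25% as excluding a loss of more than 25 points, not as equal effectiveness, which is the language of the rationale in protocol section 2.
6. State beside the 5% comparison that it needs about 322 per arm at 93% success (one-sided 5%), so that missing it is inconclusive.

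The cost is SAP and protocol wording, retrieval of the dated SAP versions, and a less favourable headline. No patients and no new data are needed.

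### The protocol's 5% and the SAP's 25% non-inferiority limits conflict and neither is justified; the 25-point limit behind N = 26 counts a true Floseal failure rate up to just under 32% as non-inferior to an assumed 7%.

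*SAP*

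**What the plan says.** Section 7.3 of the protocol (Significance) gives "a power of 0.8, a non-inferiority limit of 5% and a significance level of P < 0.05". Section 7.2 plans 60 patients, 30 per arm. No success rate is stated with these figures, and no reason is given for 5%.

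The SAP, under Sample Size, has a "non-inferiority limit (d) set at 25" percent, with a "significance level (α) of 5% and power of 80" percent. It adds: "We assumed that success in each group will be approximately 93" percent. It also says "Attrition will be assumed to be 0% due to the short duration of treatment" and concludes "This should yield 26 participants with 13 patients in each study arm".

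Under Statistical Analysis of Clinical End-points, the SAP explains why a non-inferiority design was chosen: better comfort and possibly lower cost are expected, so Floseal would be preferred if non-inferiority on hemostasis were shown. It continues that "we do not anticipate a significant difference in terms of efficacy between these two groups". The only test it names for dichotomous outcomes is Fisher's exact test. Section 7.1 of the protocol names a chi-square test. Neither document specifies a confidence interval or a test against the limit.

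Section 7.5 of the protocol promises that changes to the statistical plan will be disclosed and justified in the protocol and the final report. The protocol supplied contains no justification for a change from 5% to 25%.

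**The concern.** In a non-inferiority trial the limit defines the claim: a positive result means that a loss of that size or more has been ruled out, and nothing finer. Here the two documents define the claim differently, by a factor of five, so the same data could be non-inferior under one and not under the other.

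The SAP's supporting sentences do not fill the gap. Expecting no difference in efficacy is a statement about the likely truth, not about how much hemostasis may be given up. Comfort and cost are a reason to accept some loss, but they do not lead to 25 points. Section 2 of the protocol argues from equal effectiveness, and the SAP would make Floseal the preferred option on non-inferiority without mentioning the size of the margin. A reader of the final report could take non-inferior to mean about as good as packing, when the limit excludes only a loss of one extra failure per four patients (1/0.25).

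**Working it through.** **Inputs.** From the SAP: success p = 0.93 in both arms, limit d = 0.25, α = 5% (sidedness not stated), power 80%, attrition 0%, 13 per arm. From the protocol: limit 5%, power 0.8, P < 0.05, 30 per arm. Failure means that additional measures were needed to stop bleeding (protocol 5.1).

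**1. Reproducing the SAP's sample size.** With a true difference of zero and unpooled variance,

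n per arm = (z₁₋α + z₀.₈)² × 2p(1 − p) / d²

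- One-sided 5%: (1.645 + 0.842)² × 2 × 0.93 × 0.07 / 0.25² = 12.9, so 13 per arm and 26 in total. This matches.
- One-sided 2.5%: 16.4, so 17 per arm and 34 in total. This does not match.

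The SAP therefore uses 25 absolute percentage points at one-sided 5%.

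**2. What the limit accepts.** Boundary success is 93 − 25 = 68%, so boundary failure is 7 + 25 = 32%. The ratio is 32/7 = 4.6. True rates below that boundary count as non-inferior.

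**3. The protocol's limit on the same assumptions.** With d = 0.05 at one-sided 5%, n = 322 per arm, or 644 in total (818 at one-sided 2.5%). Approximate power against 5 points at one-sided 5% is 19% with 30 per arm and 13% with 13 per arm. The protocol's 60 patients therefore do not fit its own 5% limit at 93% success.

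**4. Chance of a non-inferiority verdict at 13 per arm.** Exact binomial enumeration, packing at 7% failures, 25-point limit, one-sided 5%; the range runs from the Farrington-Manning score rule to the Wald rule:

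| True Floseal failure rate | Chance of passing |
|---|---|
| 32% | 4% to 8% |
| 25% | 10% to 18% |
| 20% | 18% to 30% |

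**5. What particular results would exclude.** The score column is the smallest margin met at one-sided 5%. The Wald column is the loss at the lower one-sided 95% limit.

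| Floseal v packing successes | Score | Wald |
|---|---|---|
| 12/13 v 12/13 | 21.9 points | 17.2 points |
| 12/13 v 13/13 | 28.2 points | 19.9 points |
| 11/13 v 12/13 | 31.4 points | 28.2 points |
| 9/13 v 12/13 | 47.7 points | 47.4 points |
| 13/13 v 13/13 | 17.2 points | 0 (degenerate) |
| 30/30 v 30/30 | 8.3 points | 0 (degenerate) |

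Identical results of 12/13 pass the 25-point limit, yet by the score method a 21-point loss is not excluded. The result 12/13 v 13/13 passes by Wald and fails by score, so the interval method must be named in advance.

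**6. What the named test would show.** Fisher's exact test compares the arms with zero difference, not with the limit. With 6/13 failures (46%) against 1/13 (8%), p = 0.073. If a non-significant result were read as non-inferiority, that outcome would pass.

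**The case against.** **The limit is not as lenient in use as 32% suggests.** This stands. The 32% is the true rate that a positive result must exclude, not an observed rate that would pass. A reader might infer that Floseal could show about 32% failures and still be called non-inferior. The working shows otherwise: 9/13 v 12/13 (31% v 8% failures) is far outside the limit, and with one packing failure at most one Floseal failure passes.

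**Comfort and cost justify accepting some loss, and failures are rescued.** This stands in part. The SAP does give the trade-off, and section 4.4 of the protocol provides further measures when hemostasis is not achieved. Neither document turns this into a figure.

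**A reader might infer that 25 points is too large.** The documents do not support that. The size of a tolerable loss is a clinical judgement, and they state no maximum. The protocol's 5% cannot serve as the yardstick, because it too has no rationale and does not fit the protocol's own 60 patients.

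**A reader might want the word non-inferior reserved for 5%.** That would tie the term to an equally unexplained figure. By the score method even 13/13 v 13/13 (17.2 points) and 30/30 v 30/30 (8.3 points) miss it.

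**A reader might infer from the dates that the limit was relaxed late.** The protocol is dated June 2015, and the SAP is dated August 2015 and modified in October 2018. The documents do not say what was modified or when 25% was set, so this cannot be concluded.

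**Conclusion.** The concern holds in this form: two conflicting limits, 5% and 25%, neither justified. On the SAP's assumptions, its limit treats a true Floseal failure rate of up to just under 32% as non-inferior to packing at 7%, a ratio of up to 4.6. This rests on 93% success with packing, on 25% being an absolute difference, and on one-sided 5%. The last two are not stated but are implied by the exact match to 13 per arm.

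The matter affects what the trial can conclude. Without one agreed limit and a confidence limit set against it, a reader cannot tell which loss a non-inferiority statement has excluded. The finding does not extend to saying that 25 points is unacceptable or that 5 points is right.

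**What to change.** 1. Reconcile section 7.3 of the protocol with the Sample Size section of the SAP to one primary limit, and state the clinical reason for it, including how comfort and cost enter. Record the change and its reason as section 7.5 of the protocol requires.
2. In the SAP, add as the primary result the difference in hemostasis success (Floseal minus packing) with its lower one-sided 95% confidence limit, shown against both 25 and 5 points. Name the interval method; a score method such as Farrington-Manning avoids the degenerate Wald limit when no failures occur.
3. If 25 points remains the primary limit, word any positive conclusion as: *non-inferior within a margin of 25 percentage points (true failures up to 32% against an assumed 7% not counted as inferior)*. If another limit is chosen, use the corresponding figures.

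**Cost.** Text in the protocol, SAP and report. The reporting changes need no more patients. The downside is a less favourable headline. If the sponsor makes 5 points the primary limit, it should also say that neither 26 nor 60 patients gives adequate power at 93% success (about 13% and 19%).

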7.1 Statistical Methods

As this study is comparing a single experimental group to a control group we will use a standard statistical analysis to compare both the primary outcome of hemostasis and the secondary outcome results of the pain and comfort questionnaire. This is a non-inferiority study and has been powered as such. We will use a chi-square test to determine significance of any difference between the treatment and control group.

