7.2 Subject Population(s) for Analysis

We hope to have 60 patients total enrolled in this study (30 Floseal and 30 control). This sample size was chosen to provide the powering listed below. This level of significance is based on a non-inferiority trial. We chose this trial type because we seek to quantify the secondary benefits for this treatment, which is already in use. All randomized subjects will be included in the statistical analysis based on an intention-to-treat protocol.

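### The SAP names no test of its 25-point margin, and 13 per arm cannot give 80% power at one-sided 5%: the ceiling is about 63%

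*SAP*

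**What the plan says.** The SAP (Sample Size) takes a margin of 25%, a "significance level (α) of 5% and power of 80"%, success of about 93% in each group and no attrition. Its result is "This should yield 26 participants with 13 patients in each study arm". It does not say whether alpha is one-sided or two-sided.

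The SAP (Statistical Analysis of Clinical End-points) calls the trial non-inferiority and makes Floseal the preferred option if non-inferiority on hemostasis is shown. The only method it gives for an outcome of that type is: "All dichotomous categorical variables will be analyzed by means of the Fisher's exact test". No margin-shifted test, confidence interval or decision rule is attached to the 25 points.

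The protocol does not fill the gap. Section 7.1 says "We will use a chi-square test to determine significance of any difference between the treatment and control group". Sections 7.2 and 7.3 give a different design: "We hope to have 60 patients total enrolled in this study (30 Floseal and 30 control"), and "This is a non-inferiority trial with a power of 0.8, a non-inferiority limit of 5% and a significance level of P < 0.05".

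**The concern.** A non-inferiority claim needs a test, or a confidence limit, set against the margin. Fisher's exact test and the chi-square test take equality as the null hypothesis. A non-significant result from either is not evidence of non-inferiority, and a small trial makes such a result likely whatever the truth. Since the SAP also expects no significant difference in efficacy, p above 0.05 could easily be taken as the answer to the primary question.

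The sample size raises a separate doubt. At 93% success, 13 patients are expected to yield 13 × 0.07 = 0.91 failures per arm. A normal approximation is unreliable there, so the stated alpha and power may not hold together. If they do not, the trial either declares non-inferiority too easily or misses it much more often than the planned 20%.

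**Working it through.** **Inputs.** From the SAP: margin 0.25, success 0.93 in both arms, alpha 0.05, power 0.80, 13 per arm. From the protocol: 30 per arm, limit 5% (read here as 5 points).

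**1. Reproduce the SAP's figure.** The unpooled normal formula is n = (z_α + z_β)² × 2p(1 − p) / margin².

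- One-sided 5%: (1.645 + 0.842)² × 2 × 0.93 × 0.07 / 0.25² = 12.88, so 13.
- One-sided 2.5%: with 1.960 in place of 1.645, 16.35, so 17.

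The SAP's 13 is therefore correct arithmetic for this formula at one-sided 5%.

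**2. What that rule does at 13 per arm.** All 14 × 14 outcomes were enumerated with exact binomial probabilities. Type I error is taken where Floseal is exactly 25 points worse, over packing rates from 25% to 100%. The Wald rule has:

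- power 81.0% at 93% in both arms;
- type I error 7.6% at 93% vs 68%;
- maximum type I error 12.7%, at packing 100% and Floseal 75%.

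It reaches 80% power only by exceeding 5% error.

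**3. A check by hand.** With packing at 100% and Floseal at 75%, P(Floseal 12/13) = 13 × 0.25 × 0.75¹² = 0.103. That already exceeds 0.05, so no non-randomised 5% rule may accept 12/13 against 13/13. (Adding P(13/13) = 0.75¹³ = 0.024 gives the Wald maximum of 0.127.) A monotone rule is one that, if it accepts a result, also accepts any result at least as favourable to Floseal. Such a rule must then reject every Floseal result below 13/13 when packing is 13/13. With 0.93¹³ = 0.389, power is at most 1 − 0.389 × (1 − 0.389) = 0.762. This one constraint puts 80% out of reach.

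**4. The ceiling.** An integer program over all monotone rejection regions, solved to optimality, gives at most 63.2% power at one-sided 5%. Dropping monotonicity gives 63.3%; allowing randomised tests gives 67.0%.

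**5. Usable tests at 13 per arm, 25-point margin, 93% in both arms.**

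| Exact unconditional test | Power, one-sided 5% (max. type I) | Power, one-sided 2.5% (max. type I) |
|---|---|---|
| Score (Farrington-Manning) ordering | 63.2% (4.7%) | 32.7% (2.1%) |
| Unpooled-Z ordering | 62.4% (3.7%) | 47.9% (2.4%) |
| Ceiling, non-randomised monotone | 63.2% | 48.7% |

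Score ordering at one-sided 5% has power 48%, 56%, 63% and 69% at true success of 85%, 90%, 93% and 95%.

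**6. Fisher's test in place of a margin test.** With true rates of 68% vs 93%, exactly at the margin, two-sided p ≥ 0.05 occurs in 80.4% of trials at 13 per arm and 40.8% at 30 per arm. With packing at 13/13, the score-ordered exact test requires Floseal 13/13. Fisher's test stays non-significant down to 9/13 (p = 0.096), where the observed difference is 4/13, or 31 points.

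**7. If the protocol's 30 per arm governs.** Score-ordered exact power is 94.9% against 25 points but about 13% against 5 points, with 93% success assumed. The normal formula at 5 points gives 322 per arm.

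**The case against.** The arithmetic is not a slip: the formula gives 13, and the Wald rule behind it does have 81% power. The SAP states a nominal alpha and does not promise strict control along the whole null boundary. That explains where 13 came from, but it does not rescue the pair of figures. With error controlled only at the single point 93% vs 68%, the best monotone test reaches 77.2%, a much smaller shortfall but still below 80%. Requiring control for packing rates from 90% to 96% brings the ceiling back to 63.2%. The 93% is approximate, but the ceiling is 76.2% at 97% success and passes 80% only near 98% (81.6%).

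The power fault also depends on which document governs. With 30 per arm and the 25-point margin there would be no shortage of power. This objection stands, and the conclusion below carries that condition. The missing margin test does not depend on it.

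Finally, the SAP nowhere says that a non-significant Fisher result will count as non-inferiority. That is true: the fault is an omission, and the 80.4% shows what would follow if the named test were left to fill it.

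**Conclusion.** Both faults hold.

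- **Missing margin test.** Neither document names an analysis that tests a margin, so the primary conclusion has no prespecified basis at any sample size.
- **Overstated power.** If the SAP's 26 patients and 25-point margin govern, and both treatments succeed in 93%, a non-randomised monotone test that holds one-sided 5% misses non-inferiority in at least 37% of trials, against the planned 20%. At one-sided 2.5% the best such test has 48.7% power.

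The power figures rest on full binomial enumeration, type I error controlled over all packing rates from 25% to 100%, and the SAP's zero attrition.

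**What to change.** In the SAP:

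- State that alpha is one-sided 5%, the only reading that reproduces 13 per arm.
- For hemostasis, name the exact unconditional non-inferiority test against the 25-point margin with score (Farrington-Manning) ordering. Equivalently, compare with −25 points the lower limit of the two-sided 90% interval obtained by inverting that test.
- Keep Fisher's test for descriptive comparisons.
- Restate power at 13 per arm as about 63% at 93% success, with 48%, 56% and 69% at 85%, 90% and 95%.
- If one-sided 2.5% is meant, give the power of the test actually named: 33% with score ordering, 48% with unpooled-Z ordering. At that level the score-ordered test cannot declare non-inferiority even when both arms are 13/13, so the choice of ordering matters.

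In the same amendment, reconcile the protocol's 60 patients, 5% limit and chi-square test (sections 7.1 to 7.3) with the SAP. Section 7.5 already requires this: "Any deviation from the original statistical plan will be amended and justified in the protocol and in the final report". Section 10 adds: "This protocol and any amendments will be submitted to the University of Alberta HREB for formal approval to conduct the study".

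The cost is SAP wording, a less favourable stated power, a protocol amendment and an ethics board submission. No new patients are needed. If 80% power is to be kept instead, the score-ordered test needs 19 per arm (81.1%), 38 in total.
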